7.3 Recruitment

Eligible patients will be identified and approached initially by their clinical care team, and volunteers will be identified and approached by the UHS voluntary services manager before being approached by the research team (details below).

7.3.1 Sample identification

Patients: Older adults on acute medical wards at UHS will be informed about the opportunity to participate in the study by ward staff. The clinical care team will identify eligible patients for participation in the research in line with inclusion criteria through existing access to their medical records. Ward staff will liaise closely with the research team to inform them of interested participants. Patients interested in the study will then be approached by the research team who will complete informed consent and additional screening checks to determine their suitability to participate in the study, including the clinical frailty scale (CFS).

The CFS is a judgment-based frailty tool that evaluates specific domains including comorbidity, function and cognition to generate a frailty score on a 9-point scale ranging from 1 (very fit/robust and active) to 9 (terminally ill) [78]. The CFS is a valid and reliable measure of frailty in older people and is associated with a range of clinical outcomes including comorbidity, falls, cognition, function, and mortality [79]. Patients scoring ≥5 on CFS will be eligible to participate in the study.

Volunteers: Volunteers will be identified by hospital voluntary services within the UHS patient support hub, managed by [name]. The patient support hub helps ensure patients with a range of needs are supported in their own homes following discharge from hospital, including providing food parcels, and befriending services. The patient support hub recruits volunteers with an interest in supporting patients post-discharge with practical and emotional support. The research team will liaise closely with the patient support hub in the recruitment and support of volunteers interested in participating in the Frail2Fit study. The support hub team will identify and approach existing patient support hub volunteers to invite them to the study. All volunteers associated with the support hub will have appropriate clearance and training from UHS. Interested volunteers will be approached by the research team with a participant information sheet and if they meet eligibility criteria (i.e., no contraindications to the exercise component) they will complete informed consent. Two volunteers will be matched based upon volunteer experience levels to deliver the Frail2Fit intervention to a group of 5-6 participants (i.e., any newer volunteers will be matched with experienced support hub volunteers).

7.3.2 Consent

The clinical care team, or volunteer services manager will inform the research team of any interested patients and volunteers, respectively. Interested participants will then be approached by the research team to explain the study in more depth and given a participant information sheet. If the participants are still keen to volunteer following response to any of their questions and explanation of the participant information sheet, then they will complete a written consent form.

Participants will be given 2 days to decide if they would like to volunteer in the study. This will give participants time to consider their involvement in the study, to discuss the study with family and to ask any questions, while also enabling recruitment for the study before patients are discharged. All members of the study team are adequately trained in Good Clinical Practice (GCP) and have experience taking informed consent in previous research.

8 ETHICAL AND REGULATORY CONSIDERATIONS

8.1 Assessment and management of risk

There are minimal risks involved in this study. This study does not involve any invasive procedure. It is perceived that the benefits of the intervention outweigh potential risks. Studies have shown that exercise training and nutrition support are beneficial in improving physical function of older people. One of the benefits of taking part in the study is that volunteers and patients will be taught evidence-based exercises and nutrition advice which will be conducted in group online sessions. Moreover, exercising in an online group can also be a positive experience as the social aspect of group exercises has been shown to be a source of motivation.

Although the risks involved in the study are minimal, common injuries that may occur during exercises include muscle strain and back pain. Nevertheless, these risks will be reduced through various approaches explained below. Hospital volunteers are covered by NHS indemnity insurance in the case of any adverse events.

- Volunteers will complete evidence-based training modules to ensure they are competent to deliver the intervention to frail older adults. All volunteers recruited by voluntary services at the hospital have completed generic safety checks (e.g., criminal record checks) and basic training (e.g., health and safety).
- Volunteers will be taught to encourage participants to exercise at their own pace, to rest when they need to, and to move within a pain-free range of motion, ensuring that participants are working at a tailored intensity.
- Throughout the study period, fidelity checks will be conducted by the trainers once every 2 weeks to ensure that the volunteers are delivering high quality group sessions. The volunteers will be observed and assessed against a competency and implementation checklist, including competency checks for the exercise, nutrition, and behaviour change components.
- Volunteers will complete a pre-session screening checklist to ensure participants are safe to exercise (e.g., safe set-up of a home exercise space; feeling well; no new or worsening symptoms).
- Where possible participants will be encouraged to undertake the sessions with friends or family members present and they will be asked to keep cameras on during the sessions.
- If a participant feels unwell a Zoom breakout room will enable the participant's well-being to be reviewed in private by a second volunteer.
- If an emergency occurs, such as an acute medical event during the session, the volunteer will encourage participants to call their GP, or 111. If concerned about collapse, the volunteer will call 999.
- Volunteers will have a list of participant's addresses and GPs to hand in case of collapse. An
 'escalation plan' giving clear steps to follow, depending on the emergency situation, will be
 given to volunteers.
- Volunteers will be trained to support participants using the nutrition wheel and will not be
 expected to give participants specialised nutrition advice. Volunteers will be trained to
 effectively and safely signpost participants to suitable resources and health professional
 support based upon answers given from the nutrition wheel.

A potential burden for some patients could be issues with learning new technology or having minor difficulties in accessing Zoom from home. To address equality of access, participants will be provided with a tablet with the online teleconferencing platform preloaded. The tablet will contain a SIM card which will enable internet access at home, particularly for participants who do not have internet

access. The research fellow will act as a digital champion who will support individuals with low confidence to access the teleconferencing platform. Upon recruitment, participants will be taught how to use the tablet and to access the teleconferencing platform during their hospital stay. Digital support will be available to participants throughout the trial.

Participants will be given the option to choose between the online intervention and telephone consultations. Participants who opt for telephone consultations will be encouraged by volunteers to perform the exercises provided in the booklet and will be given nutritional advice. The frequency of telephone consultations will be similar to the online intervention.

Previous research (the ImPACt study) has gained feedback from interviews with volunteers and found some volunteers experienced an increased sense of purpose and belonging and improved confidence through leading the health intervention with older adults. Nevertheless, some volunteers described a small burden level, especially if they were volunteering on their own. In response to this feedback, we will ensure that 2 volunteers will be allocated per group of 5-6 participants, so the volunteers can provide support to each other during the sessions and can 'cover' each other if they are unavailable. Two volunteers to each group worked better in previous research (the ImPACt study) and helped to reduce any burdens the volunteers might have felt having to support and lead the group on their own. In addition, the trainer will supervise the volunteers closely during the first month of the intervention to ensure they are adequately supported, confident and competent to deliver the intervention. The trainer will be freely available throughout the study to support volunteers, including provision of extra one-to-one training sessions and regular monthly volunteer catch-up meetings to ensure that the volunteers are flourishing.

8.2 Research Ethics Committee (REC) and other Regulatory review & reports

This study will require ethical approval from the Health Research Authority (HRA). We will submit this study for review to the HRA NHS Research Ethics Committee through the Integrated Research Application System.

- Substantial amendments that require review by NHS REC will not be implemented until
 that review is in place and other mechanisms are in place to implement at site.
- All correspondence with the REC will be retained.
- It is the Chief Investigator's responsibility to produce the annual reports as required.
- The Chief Investigator will notify the REC of the end of the study.
- An annual progress report (APR) will be submitted to the REC within 30 days of the anniversary date on which the favourable opinion was given, and annually until the study is declared ended.
- If the study is ended prematurely, the Chief Investigator will notify the REC, including the reasons for the premature termination.
- Within one year after the end of the study, the Chief Investigator will submit a final report with the results, including any publications/abstracts, to the REC.

Discontinuation/Withdrawal of Participants from Study:

Each participant has the right to withdraw from the study at any time and request that any data collected be deleted. It will not be possible for the participant to withdraw their data once the analysis has started because the data collected will already be pseudonymised and have been used.

Participants can withdraw from the study without giving a reason by contacting the research team.

Regulatory Review & Compliance

Before any site can enrol participants into the study, the Chief Investigator/Principal Investigator will ensure that appropriate approvals from participating organisations are in place. Specific arrangements on how to gain approval from participating organisations are in place and comply with the relevant guidance.

For any amendment to the study, the Chief Investigator/Principal Investigator, in agreement with the sponsor will submit information to the appropriate body in order for them to issue approval for the amendment. The Chief Investigator/Principle Investigator will work with sites (R&D departments at NHS sites as well as the study delivery team) so they can put the necessary arrangements in place to implement the amendment to confirm their support for the study as amended.

Amendments

If the sponsor wishes to make a substantial amendment to the REC application or the supporting documents, the sponsor must submit a valid notice of amendment to the REC for consideration. The REC will provide a response regarding the amendment within 35 days of receipt of the notice. It is the sponsor's responsibility to decide whether an amendment is substantial or non-substantial for the purposes of submission to the REC.

Amendments also need to be notified to the national coordinating function of the UK country where the lead NHS R&D office is based and communicated to the participating organisations (R&D office and local research team) departments of participating sites to assess whether the amendment affects the NHS permission for that site. Note that some amendments that may be considered to be non-substantial for the purposes of REC still need to be notified to NHS R&D (e.g. a change to the funding arrangements).

The amendment history will be tracked through allocating version numbers and dates to the protocol and any study resources, which will be kept on electronic file by the CI and study sponsors.

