Volunteers will be given a training manual to help support their learning and to be used as a resource during delivery of the intervention. Volunteers will also be asked to keep an attendance record during the intervention using session completion logs and will be trained to report any adverse events.

Safety during sessions

Volunteers will be encouraged to complete a pre-session screening checklist to ensure participants are safe to exercise (e.g., safe set-up of a home exercise space; feeling well; no new or worsening symptoms). Volunteers will be taught to encourage participants to exercise at their own pace, to rest when they need to, and to move within a pain-free range of motion, ensuring that participants are working at a tailored intensity. Where possible participants will be encouraged to undertake the sessions with friends or family members present and they will be asked to keep cameras on during the

sessions. If a participant feels unwell a Zoom breakout room will enable the participant's well-being to be reviewed in private by a second volunteer.

If an emergency occurs, such as an acute medical event during the session, the volunteer will encourage participants to call their GP, or 111. If concerned about collapse, the volunteer will call 999. Volunteers will have a list of participant's addresses and GPs to hand - in case of collapse. An 'escalation plan' giving clear steps to follow, depending on the emergency situation, will be given to volunteers.

Data Collection

Participant characteristics including age, gender, domicile status, weight, body mass index, malnutrition status (MUST), baseline nutritional status (e.g., use of nutritional supplements and dietician support), co-morbidities (Charlson Co-morbidity Index) [57], cognition (Mini-mental state examination; MMSE) [58] and number of medications will be recorded. Volunteer characteristics recorded will include age, occupation, qualifications, volunteering experience, and employment status.

The primary outcome measures are feasibility and acceptability of the intervention.

Feasibility

The feasibility of implementing a volunteer-led online multi-modal intervention will be assessed by determining the number of volunteers recruited, trained and retained at the end of the study, the number of intervention sessions delivered and fidelity of volunteer delivery. Moreover, participant recruitment, retention and adherence to the intervention will be measured, as well as any adverse events

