8.6 Data protection and patient confidentiality

The study staff will ensure that the participants' anonymity is maintained. Data will be identified only by a participant ID number. All documents will be stored securely and only accessible by study staff and authorised personnel. The study will comply with GDPR and the Data Protection Act 2018, which requires data to be anonymised as soon as it is practical to do so.

Participation and all the information collected about participants during the course of the research will be kept strictly confidential. Only members of the research team and responsible members of the University of Southampton may be given access to participant data for monitoring purposes and/or to carry out an audit of the study to ensure that the research is complying with applicable regulations. Individuals from regulatory authorities (people who check that we are carrying out the study correctly) may require access to participant data. All of these people have a duty to keep participant information strictly confidential.

Data collected will be entered electronically on to a computer and stored on the university's networked storage. Access to this information will be password-protected. Hard copies of participant information will be stored in a locked filing cabinet in a secure office in our research unit and will be accessible only by the research team. Audio recordings for the interviews will be deleted once they have been transcribed. Codes are allocated to each participant to ensure that the data is anonymised. Only the researchers in this study will have access to the data. In accordance with regulations

we are required to keep participant data secure for 10 years. The data may be used in future studies by our research team. If this happens, participant data will be used anonymously (non-identifiable participant information) so participants cannot be identified. Any new research studies using participant data will be authorised by the local research ethics committee.

All participants will be made aware of the information collected during the research study during processes of informed consent through participant information sheets, discussions with the research team and completion of consent forms.

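### Until analysis starts, withdrawing participants may have any collected data deleted, and the plan does not protect the retention, adherence and adverse-event counts that form part of the primary outcome

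*Combined protocol and SAP*

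**What the plan says.** Section 8.2, under the heading on discontinuation and withdrawal, gives the rule: "Each participant has the right to withdraw from the study at any time and request that any data collected be deleted". The limit follows at once: "It will not be possible for the participant to withdraw their data once the analysis has started". The start of analysis is neither dated nor defined. No reason is required: "Participants can withdraw from the study without giving a reason by contacting the research team".

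Section 5 sets the outcomes: "The primary outcome measures are feasibility and acceptability of the intervention". On the patient side, feasibility means that "participant recruitment, retention and adherence to the intervention will be measured, as well as any adverse events". On the volunteer side it includes the numbers recruited, trained and retained. Adherence rests on attendance data: "Volunteers will also be asked to keep an attendance record during the intervention using session completion logs".

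The quantitative analysis plan in section 5 promises counts and percentages but names no denominator. Section 8.6 requires participant data to be kept for 10 years and does not mention people who withdraw. Section 7.3.2 uses the word participant for patients and volunteers alike, so the deletion right reads as covering both.

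**The concern.** The deletion right is not limited by type of data. As written it reaches session logs and adverse-event entries, not only questionnaires, accelerometer files and interviews. In a feasibility study, the records of people who leave are among the most informative results: how many sessions they attended, whether anything went wrong, and why they stopped. If those records go and the denominators shrink with them, the intervention can look better attended and better retained than it was.

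Section 4.2 says the results will help decide whether the intervention merits further evaluation, how large a controlled trial should be, and whether it suits roll-out across Wessex. With 23 patients and 6 volunteers, a few deletions move the percentages visibly.

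**Working it through.** **Inputs from the documents.** 23 patients and 6 volunteers (section 7.2.1). At most 24 sessions (section 5, Intervention); this reproduces as 4×3 + 4×2 + 4×1 = 24. The 23 is a pragmatic choice with no formula behind it, so there is no calculation to reproduce. No withdrawal rate, deletion rate or retention target is given.

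**Assumptions.** Of 23 patients, w withdraw, and d of those have their records deleted and dropped from the denominator. Stayers attend 18 of 24 sessions and leavers 6 of 24. Four patients have an adverse event. All of these are illustrative.

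**1. Retention.** With records kept it is (23 − w)/23. With d deleted it is (23 − w)/(23 − d).

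| Withdraw | All records kept | Some deleted | All leavers deleted |
|---|---|---|---|
| 2 | 21/23 = 91.3% | 1 deleted: 21/22 = 95.5% | 21/21 = 100% |
| 5 | 18/23 = 78.3% | 2 deleted: 18/21 = 85.7% | 18/18 = 100% |
| 6 | 17/23 = 73.9% | 3 deleted: 17/20 = 85.0% | 17/17 = 100% |
| 9 | 14/23 = 60.9% | 4 deleted: 14/19 = 73.7% | 14/14 = 100% |

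If the denominator stays at 23, deletion does not change retention at all. For scale, the exact 95% interval for 18/23 is 56.3% to 92.5%.

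**2. Volunteers.** One leaver of six: 5/6 = 83.3% with the record kept, 5/5 = 100% with it deleted.

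**3. Adherence, with w = 6.**
- All records: (17×18 + 6×6)/(23×24) = 342/552 = 62.0%.
- Three leavers deleted: (17×18 + 3×6)/(20×24) = 324/480 = 67.5%.
- All six deleted: (17×18)/(17×24) = 306/408 = 75.0%.

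The rise depends on leavers having attended less than stayers. Keeping a bare tally of 23 enrolled would not prevent it, because the attendance data themselves are gone.

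**4. Adverse events, with three leavers deleted.** All records: 4/23 = 17.4%. If two of the four affected patients are among those deleted: 2/20 = 10.0%. If none is: 4/20 = 20.0%. The number of patients affected can only stay the same or fall; the proportion can move either way.

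**5. Recruitment.** If deleted people leave the counts, the number recruited falls from 23 to 20, which is unfavourable to the study.

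**The case against.** Much can be said for the plan. Deletion happens only on request and only before analysis, so it affects a subset of leavers. Section 8.2 does not say that the fact of enrolment or withdrawal is erased. A non-identifying tally could survive, and the volunteer data sheet has a field for reasons for leaving, so exits are meant to be recorded. Every withdrawal and deletion count above is assumed, and with no retention threshold in the documents no changed decision can be shown. All of this stands. It does not close the gap, because the plan does not provide for such a tally, and a tally of enrolments would not preserve attendance or adverse events.

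Three stronger readings are tempting but unsupported.

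- **Every error favours the intervention.** It does not: the recruitment count would fall and an adverse-event proportion could rise. Someone who finished the sessions may also withdraw and ask for deletion.
- **A patient who gives up the sessions has no way to stay in follow-up.** Withdrawal requires contacting the research team, and nothing treats missed or stopped sessions as withdrawal. Measuring adherence presupposes that poor attenders remain in the study.
- **The cut-off contradicts the data-protection section.** Section 8.6 says "Data will be identified only by a participant ID number", so pseudonymisation alone does not mark when analysis begins. But section 8.2 also relies on the data having been used by then, which section 8.6 does not contradict. The fair criticism is that the cut-off has no date.

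**Conclusion.** The concern holds in a limited form. Before an undated start of analysis, a patient or volunteer who withdraws may ask for any collected data to be deleted. The documents supplied neither preserve a minimum record nor fix the denominators. Following the rule could selectively remove leavers' attendance and adverse-event data from the primary feasibility outcome.

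The size cannot be known from the plan. In the illustration with 6 leavers and 3 deletions, retention moves from 74% to 85% and adherence from 62.0% to 67.5%. The first figure requires the deleted people to leave the denominator; the second requires that leavers attended less. The 100% figures require every leaver to ask for deletion and are an upper limit.

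The consent and information pages were not available. If they contain protective wording, it must be reconciled with section 8.2. The point should be acted on because it touches a primary outcome in a very small study and the remedy is a change of wording.

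**What to change.** Amend section 8.2 and the information sheet to say that:

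- on withdrawal, a minimal pseudonymised record is always kept: enrolled, date stopped, sessions offered and attended, adverse events, and reason if offered;
- questionnaire, accelerometer and interview data may still be deleted on request up to a fixed date, stated in place of the start of analysis;
- all who consented, patients and volunteers, are counted in the retention, adherence and adverse-event denominators that apply to them, with the same statement added to the quantitative analysis paragraph in section 5.

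A sentence confirming that patients who stop the sessions remain due for the 3- and 6-month calls is an optional clarification.

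The cost is a slightly narrower deletion right, limited to the minimal record, and an amendment needing ethics committee review, for which section 8.2 allows 35 days for a response. No extra visits or staff are needed.
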